2.1.1 General definitions

Study drug and study treatment

For Arm A and C (monotherapy):

Study drug and study treatment both refer to LAG525 and are used interchangeably.

For Arm B (combo therapy):

Study drug refers to the individual compound i.e., LAG525 or PDR001. Study treatment refers to any combination of study drugs.

Date of first/last administration of study drug and study treatment

The date of first (last) administration of study treatment is derived as the first (last) date when a non-zero dose of any component of study treatment was administered and recorded on the Dosage Administration Record (DAR) eCRF. For the sake of simplicity, the date of first (last) administration of study treatment will also be referred as start (last) date of study treatment.

Study day

The study day for all assessments/events will be calculated using the start date of study treatment as reference. For assessments/events occurring on or after the start date of study treatment, study day will be calculated as:

Study day (days) = Event date – Start date of study treatment + 1.

Therefore, the first day of study treatment is study day 1.

For all assessment/events occurring prior to the start of the study treatment, study day will be negative and will be calculated as:

Study day (days) = Event date – Start date of study treatment.

Study day will be displayed in the data listings.

On-treatment assessment/event

An on-treatment assessment/event is defined as any assessment/event obtained in the time interval from the start date of study treatment until the last date of study treatment (i.e., including combination partner) + 30 days inclusive.

2.2 Analysis sets

The number (%) of patients in each of the defined analysis set will be summarized using the Full Analysis Set (FAS).

Full Analysis Set

The FAS comprises all patients who received at least one full or partial dose of assigned single-agent LAG525, or at least one full or partial dose of assigned combination of study drugs. Patients will be analyzed according to the planned treatment. The FAS will be used for all listings of raw data. Unless otherwise specified, the FAS will be the default analysis set used for all analyses.

Safety Set

The Safety Set includes all patients from the FAS who have received at least one dose of LAG525 or PDR001. Patients will be classified according to treatment received, where treatment received is defined as:

1. The treatment assigned if it was received at least once, or
2. The first treatment received when starting therapy with study treatment if the assigned treatment was never received.

The safety set will be used for the safety summary of the study.

Per-Protocol Set

The Per Protocol Set (PPS) consists of a subset of FAS patients in the phase II part who meet the following criteria:

- Presence of at least one measurable lesion according to RECIST 1.1 as per Study Protocol Appendix 1
- At least 2 post-baseline tumor assessments (unless disease progression according to RECIST 1.1 is observed before that time)
- Have received the planned treatment

Patients will be classified according to planned treatment.

The PPS will be used in the phase II part of the study only and will define the patients used in the sensitivity analysis of the primary endpoint. If the PPS and the FAS are identical, then analyses described by the PPS below will not be performed.

Dose- Determining Analysis Set

Single agent LAG525 escalation cohort

The dose-determining analysis set (DDS) consists of all patients from the safety set in the dose escalation part who either meet the minimum exposure criterion and have sufficient safety evaluations, or have experienced a DLT during Cycle 1.

A patient is considered to have met the minimum exposure criterion if having received at least two of the planned dose of LAG525 during Cycle 1 for Q2W schedule or at least one planned dose of LAG525 during Cycle 1 for Q4W schedule. Patients who do not experience a DLT during the first cycle are considered to have sufficient safety evaluations if they have been observed for ≥ 28 days following the first dose, and are considered by both the Sponsor and Investigators to have enough safety data to conclude that a DLT did not occur.

Combination of LAG525 and PDR001 dose escalation cohort

The dose-determining analysis set (DDS) consists of all patients from the safety set in the dose escalation part who either meet the minimum exposure criterion and have sufficient safety evaluations, or have experienced a DLT during the first two cycles.

A patient is considered to have met the minimum exposure criterion if both of the following criteria are met:

1. The patient has received at least three planned doses of LAG525 during the first 2 cycles for the Q2W schedule or at least two planned doses LAG525 during the first 2 cycles for the Q3W schedule and Q4W schedules and
2. The patients has received at least three planned doses of PDR001 during the first 2 cycles for the Q2W schedule or at least two planned doses of PDR001 during the first 2 cycles for the Q3W and Q4W schedules.

Patients who do not experience a DLT during the first two cycles are considered to have sufficient safety evaluations if they have been observed for ≥ 56 days following the first dose (42 days for patients on Q3W dosing schedule), and are considered by both the Sponsor and Investigators to have enough safety data to conclude that a DLT did not occur.

In the dose escalation part, patients who do not meet these minimum safety evaluation requirements will be regarded as ineligible for the DDS and additional patient(s) may be recruited.

Pharmacokinetic analysis set

The pharmacokinetic analysis set (PAS) consists of all patients who have at least one blood sample providing evaluable PK data. The PAS will be used for all PK analyses.

Note: Patients may be removed from the estimation of certain PK parameters on an individual basis depending on the number of available blood samples. These patients will be identified at the time of analysis.

Immunogenicity (IG) analysis sets

The Immunogenicity prevalence set includes all patients in the Full analysis set with a determinant baseline IG sample **or** at least one determinant post-baseline IG sample.

The Immunogenicity incidence set includes all patients in the Immunogenicity prevalence set with a determinant baseline IG sample **and** at least one determinant post-baseline IG sample.

The IG analysis sets will be different for LAG525 and PDR001.

See [Section 2.11.1.1](#) for the definition of determinant.

2.3 Patient disposition, demographics and other baseline characteristics

Unless noted otherwise, summaries described in this section will be based on the FAS. Summaries will be produced by treatment group or dosing regimen as appropriate and overall summary. Data will be listed individually by patient based on the FAS.

2.3.1 Patient disposition

The FAS will be used for the patient disposition summary tables and listings. The following will be tabulated:

- Number (%) of patients who discontinued treatment (based on completion of the 'End of Treatment' page with discontinuation date and reason entered),
- Primary reasons for study treatment discontinuation (based on discontinuation reason entered in the 'End of Treatment' page),
- Number (%) of patients who discontinued from study (based on completion of the 'Study evaluation completion' page with discontinuation date and reason entered),
- Primary reasons for study evaluation completion (based on discontinuation reason entered in the 'Study evaluation completion' page).

2.3.2 Basic demographic and background data

All demographic and background data (e.g. age, gender, race) will be listed and summarized.

Qualitative variables (e.g. gender) will be summarized by means of contingency tables for each treatment group. Quantitative variables (i.e. age, weight, and BMI) will be summarized by appropriate descriptive statistics for each treatment group.

BMI and BSA are calculated using the following formulas:

- $BMI [kg/m^2] = weight[kg] / (height[m]**2)$
- $BSA [m^2] = 234.94*(height[cm]**0.422)*(weight[kg]**0.515)/10000$

2.3.3 Medical History

Medical history and ongoing conditions will be summarized and listed. Separate summaries will be presented for ongoing and historical medical conditions. The summaries will be presented by primary system organ class (SOC) and preferred term (PT). Medical history and current medical conditions will be coded using the latest Medical Dictionary for Regulatory Activities (MedDRA) terminology available at the time of reporting. The MedDRA version

used for reporting will be specified in the CSR and as a footnote in the applicable tables/listings. Medical history and current (ongoing) medical conditions, including cancer-related conditions and symptoms will be listed.

2.3.4 Prior antineoplastic therapy

Prior anti-neoplastic therapy will be summarized for medication, radiotherapy and surgery. The number (%) of patients who received any prior anti-neoplastic medication, radiotherapy or surgery will be summarized separately.

The summary of prior anti-neoplastic medications include the total number of regimens (note: there can be more than one medication per regimen), immuno-oncology therapeutic class, setting at last medication, best response at last medication (defined to be the best response during the last treatment regimens recorded) and time (in months) from start of last medication to progression. The last medication is defined based on the last start date of all prior regimen components. Prior antineoplastic medications is also summarized by Anatomical Therapeutic Chemical (ATC) class, and preferred term.

The summary of prior anti-neoplastic radiotherapy will include the radiotherapy locations, (including all locations recorded for each patient), setting at last radiotherapy and method.

The summary of prior anti-neoplastic surgery will include the time (in months) between the last surgery (non-biopsy procedure) to start of study treatment.

2.3.5 Diagnosis and extent of cancer

The summary of diagnosis and extent of cancer (disease history) will include primary site of cancer, details of tumor histology/cytology, histological grade, stage at initial diagnosis, time (in months) from initial diagnosis of primary site to start of study treatment, time (in months) since most recent recurrence/relapse or progression to start of study treatment, time (in months) from initial diagnosis of primary site to first recurrence/relapse or progression, current stage of cancer, current extent of disease (metastatic sites) and types of lesions (target and non-target lesions) at baseline.

2.3.6 Analysis set exclusion

Patients will be excluded from the analysis sets based on the protocol deviations and specific non-protocol deviations entered in the database. All protocol deviations and non-protocol deviations leading to exclusion from specific analysis sets will be identified before database lock. Protocol and non-protocol deviations leading to exclusion from specific analysis sets and reasons for exclusion from populations will be tabulated/listed by treatment (Phase I) /indication and treatment (Phase II).

[Table 2-1](#) displays non-protocol deviations leading to exclusion from analysis set definitions and [Table 2-2](#) displays protocol deviations leading to exclusion from analysis set definitions.

Table 2-1 Non-protocol deviation leading to exclusion from analysis set definitions

Summary of non PD	Analysis set(s) to be excluded
No valid post-baseline safety assessment	SS

Summary of non PD	Analysis set(s) to be excluded
No administration of study treatment	FAS, SS, PPS, DDS, PAS, Immunogenicity prevalence set, Immunogenicity incidence set
1. Patient, who has not experienced DLT, was not observed for ≥ 28 days (for SA) and ≥ 56 days (for Q2W/Q4W Combo) and ≥ 42 days (for Q3W Combo) following the C1D1 or had not completed the required safety evaluations for Cycle 1 or 2. Patient who has not experienced DLT and has not received appropriate number planned doses in Cycle 1/Cycle 2 (See Section 2.2).	DDS
Patient did not have at least one measurable LAG525 concentration in cycle 1	PAS
No determinant IG sample at both baseline and post-baseline	Immunogenicity prevalence set
No determinant IG sample at baseline or post-baseline or both	Immunogenicity incidence set

Table 2-2 Protocol deviation leading to exclusion from analysis set definitions

Protocol Deviation ID (DVSPID)	Summary of PD	Analysis set(s) to be excluded
INCL01	Written informed consent must be obtained prior to screen procedures.	FAS, SS, PPS, DDS, PAS, Immunogenicity prevalence set, Immunogenicity incidence set
INCL04	In the Phase II part, patient does not have at least one tumor lesion meeting measurable disease criteria as determined by RECIST v1.1.	PPS
INCL05	In the Phase II part, patient was not a patient with either NSCLC, melanoma, TNBC, RCC or Mesothelioma.	PPS

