2.5 Treatments (study treatment, rescue medication, other concomitant therapies, compliance)

Unless otherwise noted, the Safety set will be used for all treatment/medication data summaries and listings.

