2.8 Safety evaluation

The assessment of safety is based on the type and frequency of Adverse Events (AEs) as well as on the number of laboratory values that fall outside of pre-determined ranges (Common Toxicity Criteria for Adverse Events (CTCAE) grading limits or normal ranges as appropriate). Other safety data include electrocardiogram and vital signs.

The Safety set is used for summaries and listings of safety data with the exception of dose limiting toxicities (DLT) for which the DDS is used.

Differences between treatment received and intended treatment, if any, are provided in a listing.

The overall observation period is divided into three mutually exclusive segments:

1. Pre-treatment period: from day of patient's informed consent to the day before first dose of study medication,
2. On-treatment period: from day of first dose of study medication to 30 days after last dose of study medication,

3. Post-treatment period: starting at Day 31 after last dose of study medication.

Safety summaries are primarily based on all data from the on-treatment period. Following last administration of study medication, adverse events (including serious adverse events), and new antineoplastic therapies are collected for a period of 150 days. Following start of new antineoplastic therapy, only study treatment related adverse events are collected. Select summaries of related adverse events are produced for the overall period starting from the first dose of study treatment until the end of the post-treatment period.

All safety assessments are listed and those collected during the post-treatment period are flagged.

For patients who switch from single-agent LAG525 to combination with PDR001, the on-treatment period is defined from day of first dose of study medication to 30 days after the last dose of single-agent LAG525.

All safety assessments from these patients are listed and the assessments performed under combination and those collected 30 days later than the last dose of single-agent are flagged separately.

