2.8.1.2 Data analysis

Primary summary tables for AEs will include only AEs that started or worsened during the on-treatment period.

The incidence of treatment-emergent AEs (new or worsening from baseline) will be summarized by system organ class and /or preferred tem, severity (based on CTCAE grades),

type of AE and relation to study treatment by treatment group. Serious adverse events and non-serious adverse events will be tabulated.

All deaths (on-treatment and post-treatment) will be summarized. All deaths are considered to be due to study indication.

All AEs collected in the AE (e)CRF page will be listed along with the information collected on those AEs e.g. AE relationship to study treatment, AE outcome etc. AEs starting during the pre or post-treatment periods will be flagged in the listings.

AEs will be summarized by number and percentage of patients having at least one AE in each primary system organ class (SOC) and for each preferred term (PT) using MedDRA coding. Occurrences of an AE will be counted only once in the respective AE category. A patient with multiple CTCAE grades for the same preferred term will be summarized under the maximum CTCAE grade recorded for the event. AE with missing CTCAE grade will be included in the 'All grades' column of the summary tables.

In AE summaries the primary system organ class will be presented alphabetically and the preferred terms will be sorted within primary SOC in descending frequency. The sort order for the preferred term will be based on their frequency in all patients.

The following adverse event summaries will be produced by treatment for AEs starting or worsening during the on-treatment period:

- Overview of adverse events and deaths (number and % of patients who died, with any AE, any SAE, any AE leading to dose reductions/interruptions, AE leading to discontinuation)
- AEs by SOC and PT, summarized by relationship (all AEs and AEs related to study treatment);
- Seriousness (SAEs, and non-SAEs);
- Leading to treatment discontinuation;
- Leading to dose interruption/adjustment;
- Requiring additional therapy;
- Dose limiting toxicities by PT

The following listings will be produced:

- All adverse events (safety set)

Deaths (CSR Outputs)

On-treatment deaths are summarized produced by preferred term.

All deaths will be listed for the safety set, deaths occurring after the on-treatment period will be flagged.

EudraCT and clinicaltrials.gov requirements for AEs and Deaths summaries

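### SAP Table 2-1 excludes some dosed patients from the Safety Set for lack of follow-up, contradicting the exposure-only definition in protocol 10.1.2 and SAP 2.2

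*SAP*

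**What the plan says.** SAP 2.2 defines the set by exposure: "The Safety Set includes all patients from the FAS who have received at least one dose of LAG525 or PDR001". Protocol 10.1.2 uses the same sentence. Neither asks for any assessment after dosing. The FAS is also exposure-based: "The FAS comprises all patients who received at least one full or partial dose of assigned single-agent LAG525", with a parallel clause for the combination.

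SAP 2.3.6 then sets out how exclusions are applied: "Patients will be excluded from the analysis sets based on the protocol deviations and specific non-protocol deviations entered in the database". In Table 2-1 the first row reads "No valid post-baseline safety assessment", and the only set named against it is the Safety Set (SS). A separate row, "No administration of study treatment", removes undosed patients from all the analysis sets.

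The Safety Set carries most of the safety reporting:

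- SAP 2.8: "The Safety set is used for summaries and listings of safety data", with DLTs the exception.
- SAP 2.8.1.2: "All deaths will be listed for the safety set, deaths occurring after the on-treatment period will be flagged". The adverse event tables for the public registries are also specified on this set.
- SAP 2.5: "Unless otherwise noted, the Safety set will be used for all treatment/medication data summaries and listings".

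**The concern.** The SAP gives two different rules for the same analysis set. Under 2.2, every dosed FAS patient is in the Safety Set. Under Table 2-1, a dosed patient also needs some later assessment judged valid. That second condition is observed only after treatment starts, so membership can be related to outcome. A patient with nothing valid after the first infusion may well have died, deteriorated, withdrawn or been lost to follow-up.

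An all-treated safety population exists so that early events and early losses stay in both numerator and denominator. The row breaks that principle. It also lets the safety and FAS denominators differ, although the definitions give no reason for them to. And because the key term is undefined, the choice of who is dropped falls to whoever enters the deviations and programs the tables.

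**Working it through.** No design figure is involved. The check is a comparison of texts, followed by a small illustration of direction.

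**1. Membership under each rule.**

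- Definition (protocol 10.1.2, SAP 2.2): Safety Set = FAS patients with at least one dose. Taking a partial dose as a dose, this is the same group of patients as the FAS.
- Table 2-1: Safety Set = that group minus dosed patients with no valid assessment after baseline.
- Difference: exactly those patients. They stay in the FAS, because the row names only SS.

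The consent row in Table 2-2 removes a patient from the FAS and the Safety Set alike, so it does not affect this comparison.

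**2. Is the row operative, and is it reconciled anywhere?** Section 2.3.6 says that patients will be excluded on this basis. The DDS and immunogenicity rows of Table 2-1 restate conditions already in SAP 2.2; the SS row has no counterpart there. The SAP document history records that an exclusion subsection was added but no change to the Safety Set definition. Nothing else in either document resolves the conflict.

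**3. Direction of effect.** Let x of n patients have an event, and let the row remove one patient.

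- Removed patient had the event: the rate goes from x/n to (x − 1)/(n − 1), which is lower whenever x < n.
- Removed patient had no event: the rate goes from x/n to x/(n − 1), which is higher whenever x > 0.

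Illustration with the planned group sizes of about 20, extendable to 40 (SAP 2.6.2). The event counts are assumptions.

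| Case | Definition | Table 2-1 |
|---|---|---|
| Recorded events do not count as an assessment; the one death in the group is removed, n = 20 | 1/20 = 5.0% | 0/19 = 0% |
| Same, n = 40 | 1/40 = 2.5% | 0/39 = 0% |
| Recorded events do count; one event-free patient is removed, 10 with an AE, n = 20 | 10/20 = 50.0% | 10/19 = 52.6% |

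The sign depends on a definition that the SAP does not give.

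**4. How many patients?** The documents give no number. Several features of the protocol suggest very few: an ECG one hour after the first dose (Table 7-5), continuous adverse event recording (Table 7-1), safety contacts at 30, 90 and 150 days that may be by telephone (7.1.5), and a dedicated death form (8.1.1; SAP 2.8.1.1).

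**The case against.** A reader might infer that the row strips early deaths out of the report and biases adverse event and death rates downward. The documents do not support that as a general statement.

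- Protocol 7.2.2 includes adverse event collection among the safety assessments. On that reading, a patient with a recorded event after dosing has an assessment and stays in. Only event-free patients leave, and rates move slightly up. A downward bias needs a narrower reading, in which recorded events and deaths do not count, and the SAP never states one.
- A patient who receives one infusion and then dies would normally have the one-hour ECG and a death form. A death from progression may not be reported as a serious adverse event (protocol 8.1.1), but the death form still applies.
- Excluded patients would not disappear. Section 2.3.6 requires exclusions and their reasons to be tabulated or listed. Disposition (SAP 2.3.1) and raw-data listings (SAP 2.2) use the FAS, and PFS, which counts death from any cause, is analysed on the FAS (SAP 2.7.1, 2.7.2).

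All of this stands, and it limits both the size and the certainty of the effect. It does not remove the conflict between Table 2-1 and the definition. FAS outputs elsewhere do not put a patient back into a safety rate, nor into a death listing that 2.8.1.2 ties to the Safety Set.

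**Conclusion.** Wrong as written. Table 2-1 contradicts the Safety Set definition in both documents and conditions a safety population on follow-up after dosing. That conclusion rests on the text alone and is firm.

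The consequence is conditional. Early deaths or drop-outs could be lost from the safety summaries and death listing if recorded events do not count as assessments; adverse event rates could be slightly inflated if they do. Neither direction can be asserted from the documents. The number affected is unknown and probably very small, possibly zero if the first-day ECG counts.

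The response-rate analysis is on the FAS and is unaffected. The dose-determining set, although drawn from the Safety Set, is little affected: a patient with a DLT has a safety record after dosing, and one without a DLT must meet exposure and observation requirements anyway.

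**What to change.** Delete the row "No valid post-baseline safety assessment" (SS) from SAP Table 2-1. The Safety Set then matches protocol 10.1.2 and SAP 2.2, and dosed patients without later assessments stay in all safety denominators. They may be listed separately if the team wants them identified.

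The cost is one table row in a SAP amendment, plus the matching exclusion flag in the programming specifications. No new data are needed, and neither the design nor the efficacy analyses change.
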